10.3.1.1. Analysis Methods

The primary analysis for all continuous efficacy and health outcomes variables will use a mixed-effects models for repeated measures (MMRM) with treatment, [REDACTED]

[REDACTED] An unstructured covariance matrix will be used to model the within-patient variance-covariance errors. If the unstructured covariance matrix results in a lack of convergence, the heterogeneous Toeplitz covariance structure, followed by the heterogeneous autoregressive covariance structure will be used. The Kenward-Roger method will be used to estimate the denominator degrees of freedom. Type III sums of squares for the least-squares (LS) means will be used for all the statistical comparisons; the 90% confidence interval (CI) will also be reported. The LS mean difference, standard error, p-value, and CIs will also be reported. Treatment group comparisons at specific study visits will be tested using the t-test obtained from the MMRM results. Additional details of the MMRM method are described in Section 10.3.1.2.

The primary analysis for all categorical efficacy and health outcomes variables will use a logistic regression analysis with treatment, cohort, [REDACTED]

[REDACTED] The p-value and 90% (unless otherwise specified) CI for the odds ratio from the logistic regression model will be used for primary statistical inference. When logistic regression sample size requirements are not met, (<5 responders in any category for any factor), the p-value from the Cochran-Mantel-Haenszel (CMH) test with [REDACTED] [REDACTED] as factors will be used instead of the odds ratio and CI. Missing data imputation is described in Section 10.3.1.2.

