10.3.3.2. Secondary Analyses

Secondary efficacy and health outcomes variables will be assessed using the methods stated in Sections 10.3.1.1 and 10.3.1.2.

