4.1. Primary Objective

The primary objective of Study I4V-MC-JAIV (JAIV) is:

Table JAIV.4.1. Primary Objective and Endpoint

Objectives	Endpoints

 To evaluate the effect of baricitinib 4-mg QD compared to placebo on PBC disease 	
 Change from baseline in ALP at Week 12

Abbreviations: ALP = alkaline phosphatase; PBC = primary biliary cholangitis; QD = once daily.

According to ICH E9R1 guidelines, the objectives of a study should be translated into precise definition of estimands. Estimands are defined using the following four attributes:

- The population of interest consists of the patients targeted by the scientific question;
- The variable (or endpoint) of evaluation that is obtained for each patient, required to address the scientific question;
- The population-level summary of variable, a basis for treatment evaluation;
- The specification of how to account for intercurrent events to reflect the scientific question of interest.

In particular, for Study JAIV, the estimands are defined by:

- Population:** The population of interest is patients with primary biliary cholangitis (PBC) who have had an inadequate response or intolerance to ursodeoxycholic acid (UDCA). Analysis populations are defined in Section 6.1.1. The analysis population corresponding to each of the efficacy and health outcome endpoints is specified in [Table JAIV.6.3](#) and [Table JAIV.6.5](#).
- Variables:** The primary endpoint/variable is listed in [Table JAIV.4.1](#) and secondary endpoints/variables are listed in [Table JAIV.4.2](#). A full list of efficacy and health outcome endpoints/variables is given in [Table JAIV.6.2](#) and [Table JAIV.6.4](#).
- Population-level Summary:** The summary measure for binary variables will be proportion and the summary measure for continuous variables will be average. The primary comparison of interest will be the difference of proportions between baricitinib dose groups and placebo. Details are given in Section 6.7.

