6.1.3. Analysis Methods

The primary analysis for all continuous efficacy and health outcome variables will use a mixed-effects models for repeated measures (MMRM) with [REDACTED]

[REDACTED] An unstructured covariance matrix will be used to model the within-patient variance-covariance errors. If the unstructured covariance matrix results in a lack of convergence, the heterogeneous Toeplitz covariance structure, followed by the heterogeneous autoregressive covariance structure will be used. The Kenward-Roger method will be used to estimate the denominator degrees of freedom. Type III tests will be used for all the statistical comparisons; the 90% confidence interval (CI) will also be reported. The LS mean difference, standard error, p-value, and CI will also be reported. Treatment group comparisons at specific study visits will be tested using the t-test obtained from the MMRM results. Data will be censored as described in Section 6.3.

The primary analysis for all categorical efficacy and health outcome variables will use a logistic regression analysis [REDACTED]

[REDACTED] The p-value and 90% (unless otherwise specified) CI for the odds ratio from the logistic regression model will be used for primary statistical inference. When logistic regression sample size requirements are not met, (<5 responders in any category for any factor), the p-value from the Cochran-Mantel-Haenszel (CMH) test with [REDACTED]

In addition, all primary and secondary continuous efficacy and health outcome variables will use analysis of covariance (ANCOVA) models [REDACTED]

[REDACTED] and cohort in the model as a supplementary analysis. Type III sums of squares for the least-squares mean (LSM) will be used for the statistical comparison of treatment groups, and the LSM difference, standard error, p-value and 90% CI will also be reported. The last observation carried forward (LOCF) approach will be used to impute missing data.

All safety data will be descriptively summarized by treatment groups and analyzed using the safety population.

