6.10. Efficacy Analyses

The general methods used to summarize efficacy data, including the definition of baseline value for assessments are described in Section 6.1.

Efficacy will generally be analyzed from Week 0 to Week 12, and patients will be analyzed according to the investigational product to which they were randomized at Week 0 (Visit 3):

Table JAIV.6.2 includes the descriptions and derivations of the primary and secondary efficacy outcomes.

Table JAIV.6.3 provides the detailed analyses including analysis type, method and imputation, population, time point, and comparisons for efficacy analyses.

Table JAIV.6.2. Description and Derivation of Primary and Secondary Efficacy Outcomes

Measure	Description	Variable	Derivation / Comment	Definition of Missing
Alkaline Phosphatase (ALP)	Laboratory measurement of the enzymatic (catalytic) activity of ALP enzyme within the blood.	
 Change from baseline in ALP 	Change from baseline: observed ALP – baseline ALP	Missing if baseline or observed value is missing.
Total Bilirubin and Alkaline Phosphatase (ALP)	Measurement of concentration of total bilirubin in the blood and measurement of the enzymatic (catalytic) activity of ALP enzyme within the blood.	
 Proportion of patients with ALP <1.67 x ULN (and at least 15% decrease from baseline) and total bilirubin < ULN 	If observed ALP < 1.67 x ULN and $\frac{\text{baseline ALP} - \text{observed ALP}}{\text{baseline ALP}} \times 100 \geq 15$, and observed total bilirubin < ULN then conclude that the patient has ALP <1.67 x ULN (and at least 15% decrease from baseline) and total bilirubin < ULN.	Missing if any one of baseline ALP, observed ALP, or observed total bilirubin is missing.

Table JAIV.6.3. Description of Primary and Secondary Efficacy Analyses

Measure	Variable	Analysis Method (Section 6.1.3)	Population (Section 6.1.1)	Comparison/Time Point	Analysis Type
Alkaline Phosphatase (ALP) and Total Bilirubin	• Change from baseline in ALP	MMRM	mITT	Bari 4-mg vs PBO; Week 12	Primary analysis
				Bari 2-mg vs PBO; Week 12	Secondary analysis
	• Proportion of patients with ALP <1.67 x ULN (and at least 15% decrease from baseline) and total bilirubin <ULN at Week 12	ANCOVA using LOCF	mITT	Bari 4-mg vs PBO; Week 12	Supplementary analysis
				Bari 2-mg vs PBO; Week 12	Supplementary analysis
		Logistic regression using LOCF	mITT	Bari 4-mg vs PBO; Week 12	Secondary analysis

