				Bari 2-mg vs PBO; Week 12	Secondary analysis
Logistic regression using NRI	mITT	Bari 4-mg vs PBO; Week 12	Supplementary analysis		
		Bari 2-mg vs PBO; Week 12	Supplementary analysis		

Abbreviations: ANCOVA = analysis of covariance; Bari = baricitinib; mITT = modified intent-to-treat; LOCF = last observation carried forward; MMRM = mixed model repeated measures; NRI = nonresponder imputation; PBO = placebo.

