6.10.3. Supplementary Analyses

Supplementary analyses for select outcomes have been previously described and include the following:

- Non-responder imputation (NRI) (Section 6.3.3) for categorical secondary outcomes.
- Analysis of continuous outcomes with ANCOVA (Section 6.1.3), with missing data imputed using LOCF (Section 6.3.1) for continuous primary and secondary outcomes.

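### The SAP makes the difference in responder proportions the comparison of interest, but no visible text defines an estimator or interval for it, and the sparse-data fallback drops the odds-ratio interval

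*SAP*

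**What the plan says.** **Comparison of interest.** In its estimand text, SAP 4.1 takes the proportion as the summary for binary variables and adds: "The primary comparison of interest will be the difference of proportions between baricitinib dose groups and placebo". It refers the reader to Section 6.7 for details. That section is Patient Characteristics and describes no efficacy comparison.

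**Inference.** SAP 6.1.3 uses logistic regression for categorical endpoints, and the p-value and 90% "CI for the odds ratio from the logistic regression model will be used for primary statistical inference".

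**Fallback.** The same section continues: "When logistic regression sample size requirements are not met, (<5 responders in any category for any factor), the p-value from the Cochran-Mantel-Haenszel (CMH) test" is used, with the rest of the sentence redacted. In protocol 10.3.1.1 the end of the parallel sentence is visible: the CMH p-value with redacted terms "as factors will be used instead of the odds ratio and CI". Protocol 10.3.3.2 applies this to the responder endpoint: "Secondary efficacy and health outcomes variables will be assessed using the methods stated in Sections 10.3.1.1 and 10.3.1.2".

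**Listed analyses.** For the responder endpoint, SAP Table JAIV.6.3 lists "Logistic regression using LOCF" as the secondary analysis and "Logistic regression using NRI" as supplementary, for each dose against placebo. SAP 6.10.3 adds only "Non-responder imputation (NRI) (Section 6.3.3) for categorical secondary outcomes".

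**Synopsis.** The protocol synopsis names treatment, cohort, baseline ALP category and baseline UDCA use as the logistic-model terms. It says that proportions and a 90% interval will be reported, but not whether these are per arm or between arms.

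**The concern.** The stated comparison of interest and the stated inference are on different scales, and the cross-reference that should connect them leads elsewhere. An odds ratio does not give the difference in proportions without further steps, and no visible text supplies them.

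The fallback makes this matter more. A CMH p-value shows neither the size nor the precision of an effect. Once it replaces the odds ratio and its interval, the visible plan has no clearly defined between-group interval left for this endpoint. The groups are small enough for this to be a realistic outcome. The endpoint is a listed secondary endpoint for both doses, in a proof-of-concept study meant to inform benefit and risk. If nothing in the redacted text covers the case, the method for any interval would have to be chosen after the responder counts are known.

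**Working it through.** **Comparator and group sizes.** Protocol 5.2 plans about 12 patients on 2 mg, 20 on 4 mg and 20 on placebo (8 + 12 over the two cohorts). The plan gives no response rate and no power for the responder endpoint. Its only power figure, 81% for ALP change, reproduces with pooled placebo: noncentrality 65 / (80 × √(1/20 + 1/20)) = 2.57, 38 degrees of freedom, two-sided alpha 0.1, power 0.810. With the 12 Cohort B placebo patients alone it is 0.70. So pooled placebo is the plan's comparator.

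**Chance that an arm has at least 5 responders.** Exact binomial: P(X ≥ 5) = 1 − Σ(k = 0 to 4) C(n,k) p^k (1−p)^(n−k). For n = 20 and p = 0.20 the five terms are 0.0115 + 0.0576 + 0.1369 + 0.2054 + 0.2182 = 0.630, so the probability is 0.370. All rates are assumptions.

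- Placebo, n = 20: 4%, 17%, 37%, 59% and 76% at 10, 15, 20, 25 and 30%. The probability reaches 50% at a rate of 23.0%.
- 2 mg, n = 12: 16%, 28%, 56%, 70% and 81% at 25, 30, 40, 45 and 50%. The probability reaches 50% at a rate of 37.9%.
- 4 mg, n = 20: 94.9%, 99.8% and nearly 100% at 40, 55 and 60%.

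**Chance that the logistic model is kept, on the treatment factor alone.** This is the product over the arms that must pass. The documents do not say whether the trigger is judged per comparison or over all arms, so both readings are shown.

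| Assumed placebo / 2 mg / 4 mg | 4 mg vs placebo only | All three arms |
|---|---|---|
| 10 / 25 / 40% | 0.043 × 0.949 = 4% | × 0.158 = 0.6% |
| 20 / 40 / 55% | 0.370 × 0.998 = 37% | × 0.562 = 21% |
| 25 / 45 / 55% | 0.585 × 0.998 = 58% | × 0.696 = 41% |
| 30 / 50 / 60% | 0.762 × 1.000 = 76% | × 0.806 = 61% |

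These are upper limits. The rule covers every factor, so the other terms named in the synopsis can only lower them. By how much depends on the baseline ALP and UDCA mix, which the documents do not give.

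**Whether an interval for the difference is still available.** The Miettinen-Nurminen 90% interval holds every δ with |p̂1 − p̂2 − δ| / √{[p̃1(1−p̃1)/n1 + p̃2(1−p̃2)/n2] × N/(N−1)} ≤ 1.645. Here N = n1 + n2, and p̃1 and p̃2 are the maximum-likelihood rates under p1 − p2 = δ. For illustrative counts that would trigger the fallback:

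- 4 mg 8/20 vs placebo 2/20: +30.0 points (7.7 to 50.5), width 42.8.
- 2 mg 3/12 vs placebo 2/20: +15.0 points (−7.1 to 40.8), width 47.9.
- 4 mg 8/20 vs placebo 0/20: +40.0 points (24.1 to 58.4). With a 10% placebo rate, no placebo responders has probability 0.9^20 = 12%. The unadjusted odds ratio is then infinite, but the difference and its interval exist.

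Newcombe's hybrid-score method gives similar limits in the first two cases: 7.4 to 49.3 and −6.7 to 39.6.

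**The case against.** **Redaction.** SAP 6.1.3 is blacked out in two places that bear on categorical endpoints: after the logistic regression is named, and after the words introducing the CMH test. Either block could hold a difference estimate or the synopsis sentence on proportions. This stands. A reader might infer that the sponsor planned no interval for the difference. The documents do not support that; they show only that none is defined in visible text.

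**The table.** A reader might treat Table JAIV.6.3 as proof that no interval was planned. It is not. The table lists models and imputation methods, not output statistics, and it omits the CMH test although SAP 6.1.3 plans it.

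**The synopsis.** It does promise proportions with a 90% interval, so it would be wrong to say that the plan offers nothing but an odds-ratio interval. But the sentence names no method and can be read as per-arm intervals.

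**How likely the fallback is.** Requiring all three arms to pass is one reading. Table JAIV.6.3 lists the doses as separate comparisons, and for 4 mg against placebo alone the model is kept in most trials once placebo response reaches 25%. A reader might infer that the fallback is near-certain. That holds at low placebo response, not at every plausible rate.

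**Consequence.** Per-arm proportions give the point difference by subtraction, so what is at risk is the interval. Restating the SAP 4.1 summary as an odds ratio would also remove the scale mismatch, but would leave the fallback without an interval.

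**Conclusion.** The point holds for the visible text. SAP 4.1 names a difference of proportions and cites the wrong section for it. The visible inference is on the odds-ratio scale, and the protocol's fallback replaces the only between-group interval that is clearly defined with a p-value.

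On the treatment factor alone, the fallback is more likely than not below about 23% placebo response, under either reading of the trigger. Across all arms it is also more likely than not below about 38% 2-mg response. For 4 mg against placebo alone, the model is kept with probability 4% to 76% over assumed placebo/4-mg rates from 10/40 to 30/60%.

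These figures rest on assumed response rates and the planned group sizes. The redacted text could already contain a method, so confidence is moderate. The effect is confined to one secondary endpoint. The primary ALP analysis, its power and the sample size are unchanged. The change is worth making because it is cheap and brings the output into line with the SAP's own summary measure.

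**What to change.** - **SAP 6.1.3:** report the difference in responder proportions for each dose against pooled placebo, with a 90% score interval, whatever the responder counts. Miettinen-Nurminen is a suitable choice and Newcombe is also acceptable; name one. Keep the CMH p-value as the fallback test.
- **Table JAIV.6.3:** add a row for this analysis.
- **SAP 4.1:** replace the reference to Section 6.7 with the section that holds the method.
- **Optional:** add the difference against same-cohort placebo, labelled as a sensitivity analysis, because each dose is studied in one cohort only.

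If the redacted text already defines such an interval, only the cross-reference and the table row are needed. The edits can be confined to the SAP, because protocol 10.3.1.2 leaves full analysis details to it.

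The cost is a sentence, a table row, a corrected reference and a few lines of code. The downsides are that the intervals are wide, about 43 and 48 points for 4 mg and 2 mg in the first two examples, and are not adjusted for cohort, baseline ALP or UDCA use. They may therefore not agree exactly with the adjusted p-value, and the SAP should say so.

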6.2. Covariate Adjustment

The randomization to treatment groups at Week 0 (Visit 3) is stratified by [REDACTED]

The covariates used in the ANCOVA model for continuous data generally will include the parameter value at baseline. Inclusion of baseline in the ANCOVA model ensures that treatment LSMs are estimated at the same baseline value. When an MMRM analysis is performed, baseline value and baseline-by-visit interactions will be included as covariates.

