5.1. Overall Design

Study I4V-MC-JAIV (JAIV) is a multicenter, randomized, double-blind, parallel, placebo-controlled, proof-of-concept Phase II study in patients with primary biliary cholangitis (PBC) who have an inadequate response or are intolerant to UDCA that will be conducted in 2 cohorts. Both cohorts will follow the same study schedule.

Cohort A

Cohort A is a randomized, double-blind, parallel, placebo-controlled cohort comprised of the first group of patients. At least twelve patients will be randomized to baricitinib 2-mg and at least eight patients will be randomized to placebo. Once Cohort A has fully enrolled, enrollment will be suspended.

Once all Cohort A patients have completed the 12 week treatment period their data will be reviewed by an external DMC.

The primary goal of Cohort A will be to assess the tolerability and safety of baricitinib 2-mg compared to placebo through Week 12. Efficacy measures, such as change in ALP will also be assessed to provide context for the benefit:risk ratio.

A DMC will oversee this study (Section 9.4.8.2).

Cohort B

Cohort B is a randomized, double-blind, parallel, placebo-controlled phase comprised of the second group of patients. At least twenty patients will be randomized to baricitinib 4-mg and at least twelve patients will be randomized to placebo.

Enrollment in Cohort B will begin only after the DMC review of Cohort A is complete and Lilly has received and accepted a recommendation to proceed.

Figure JAIV.1 illustrates the study design.

All procedures to be conducted during the study, including timing of all procedures, are indicated in the Schedule of Activities (Section 2). Section 7.6 describes permitted concomitant therapy. Study governance considerations are described in detail in Appendix 3.

Each cohort of the study consists of 3 periods:

Screening Period: The screening period is up to 49 days and begins when the patient signs the informed consent form (ICF). In exceptional circumstances, the screening window can be extended after consultation with the sponsor where local authorities permit. During the screening period, the investigator must confirm the patient meets all inclusion and no exclusion criteria for the study (Section 6). Two assessments of AST, ALT, ALP, and total bilirubin values are required prior to randomization (by at least two measurements obtained at least 4 weeks apart). If the AST, ALT, ALP, or bilirubin values from the second sample are increased more

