In the case of any of the aforementioned laboratory abnormalities, the tests may be repeated once during screening, and values resulting from repeat testing may be accepted for enrollment eligibility if they meet the eligibility criterion.

- [44] The second set of screening values for ALT, AST, or total bilirubin are above the upper limit of normal **and** > 20% higher than the first values obtained during screening
- [45] The second screening value for ALP is > 20% higher than the first value obtained during screening

Prior/Concomitant Therapy

- [30] Are receiving unstable treatment for pruritus within 6 weeks prior to Visit 3 (Week 0).
- [31] Have been treated with systemic (oral or parenteral) corticosteroids within 6 weeks prior to Visit 3 (Week 0).

Note: the use of topical, ophthalmic, intranasal, and inhaled corticosteroids will be permitted.

- [32] Have received biologic treatments for an immunologic disease within 4 weeks of screening such as etanercept, infliximab, certolizumab, adalimumab, golimumab, tocilizumab, abatacept, ustekinumab, ixekizumab, secukinumab, or anakinra.
- [33] Have received a JAK inhibitor.
- [34] Have received obeticholic acid.
- [35] Have received fenofibrate or other fibrates for the treatment of PBC.
- [36] Are currently treated with probenecid that cannot be discontinued for the duration of the study.

Other Exclusions

- [37] Are largely or wholly incapacitated permitting little or no self-care, such as being bedridden.
- [38] In the opinion of the investigator, are at an unacceptable risk for participating in the study.
- [39] Have donated more than a single unit of blood within 4 weeks prior to screening or intend to donate blood during the course of the study.

- [40] Have a history of IV drug abuse, other illicit drug abuse, or chronic alcohol abuse within the 2 years prior to screening or are concurrently using, or expected to use during the study, illicit drugs (including marijuana). Alcohol abuse is defined as consumption of more than 210 mL of alcohol per week (i.e., the equivalent of 14 four-ounce (125 mL) glasses of wine or 14 twelve-ounce (330 mL) cans/bottles of beer), or other substance abuse within 1 year prior to Visit 3 (Week 0).
- [41] Are unable or unwilling to make themselves available for the duration of the study and/or are unwilling to follow study restrictions/procedures.

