6.4. Screen Failures

Individuals who do not meet the criteria for participation in this study (screen failure) may be rescreened. Individuals may be rescreened 1 time. The interval to rescreening should be at least 2 weeks. The individual must sign a new ICF and will be assigned a new identification number at the time of the second screening.

7. Treatments

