5.2. Determination of Sample Size

Approximately 20 patients will be randomized to the baricitinib 2-mg and placebo treatment groups for Cohort A. Twelve patients will be randomly assigned to the 2-mg treatment group and 8 patients to the placebo treatment group. This sample size is appropriate to provide

sufficient preliminary safety and tolerability information for baricitinib 2-mg in patients with PBC prior to studying 4-mg baricitinib.

For Cohort B, 32 patients will be randomized to the baricitinib 4-mg and placebo treatment groups. Twenty patients will be randomized to the baricitinib 4-mg treatment group and 12 patients to placebo.

Overall, 20 patients per group will be assigned to the baricitinib 4-mg (Cohort B) and placebo (Cohorts A and B) dose groups. Based on this sample size, this study will have approximately 81% power to detect a difference in ALP change from baseline between baricitinib 4-mg and placebo at Week 12 assuming that the true difference is 65 U/L. The sample size was determined based on a 2-sample t-test with 2-sided alpha level of 0.1 and a standard deviation of 80 U/L for the change from baseline in ALP. The sample size calculation was performed using nQuery[®] Advisor 7.0 software.

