6.1.2. Definition of Baseline and Postbaseline Measures

Baseline will be defined as the last available value before the first dose of investigational product for both efficacy and safety analyses. In most cases, this will be the measure recorded at Week 0 (Visit 3). Change from baseline will be calculated as the visit value of interest minus the baseline value.

Postbaseline measurements are collected after study drug administration through Visit 7 (Week 12) or an early discontinuation visit.

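### Optional gain, not an error: the ALP model could also adjust for the mean of the two screening ALP values that are already required

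*SAP*

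**What the plan says.** - **Covariates.** SAP 6.2: "When an MMRM analysis is performed, baseline value and baseline-by-visit interactions will be included as covariates". The full list of MMRM terms is blacked out in SAP 6.1.3 and, after treatment, in Protocol 10.3.1.1.
- **Baseline.** SAP 6.1.2: "Baseline will be defined as the last available value before the first dose of investigational product for both efficacy and safety analyses". This is one value, usually from Visit 3 (Week 0).
- **Screening ALP.** Protocol 5.1: "Two assessments of AST, ALT, ALP, and total bilirubin values are required prior to randomization", at least 4 weeks apart. The Schedule of Activities has clinical chemistry at Visits 1, 2 and 3.
- **Use of those values.** Inclusion criterion 3 and exclusion criterion 29 set ALP limits, and exclusion criterion 45 compares the two screening values: "The second screening value for ALP is > 20% higher than the first value obtained during screening". No readable efficacy model uses them.
- **Planned precision.** SAP 5.2 gives 81% power for 65 U/L with 20 per group, two-sided alpha 0.1, a two-sample t-test and "a standard deviation of 80 U/L for the change from baseline in ALP".
- **Other model terms that can be read.** The supplementary ANCOVA has cohort ("and cohort in the model as a supplementary analysis"). The logistic model in the Protocol Synopsis has cohort, an ALP category split at 2.5 × ULN, and UDCA use.

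**The concern.** A single Week 0 ALP value mixes the patient's stable level with that day's fluctuation. Two earlier values of the same variable help to separate the two, and so can predict Week 12 better than Week 0 alone. Every eligible patient should already have them.

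Both values precede randomisation. Adjusting for them adds no bias to the randomised comparison within Cohort B (20 vs 12) and does not change the estimand. That does not vouch for the pooled 20 vs 20 contrast, which borrows 8 placebo patients from Cohort A.

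At stake is the width of the primary 90% CI in a study with about 20 patients per group. The stated 81% power is not in question: it comes from an unadjusted t-test.

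**Working it through.** **1. The plan's own figure.** The standard error is 80 × √(1/20 + 1/20) = 25.3 U/L, so the noncentrality is 65/25.3 = 2.57. With 38 df and two-sided alpha 0.1, the noncentral t gives 81.0%. The stated 81% reproduces.

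**2. Closed form.** Assume an equal correlation r between all ALP measurements (not given in the documents), with the SD of change held at 80 U/L.

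- SD of a single value: 80/√(2(1 − r)).
- Residual variance given Week 0: proportional to 1 − r².
- Residual variance given Week 0 and the screening mean: proportional to (1 − r)(1 + 3r)/(1 + 2r).
- Ratio: (1 + 3r)/((1 + 2r)(1 + r)).

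At r = 0.7 the ratio is 3.1/(2.4 × 1.7) = 0.76, a 24% cut in variance. The residual SD falls from 73.8 to 64.3 U/L, the 90% CI half-width from 39.3 to 34.3 U/L, and power rises from 86.2% to 93.2%. At r = 0.5 the variance cut is 17% (power 89.7% to 93.9%); at r = 0.8 it is 27% (84.5% to 92.9%).

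A value of r = 0.9 is not credible here. It needs an ALP SD of 80/√0.2 = 179 U/L, whereas even a uniform spread over 1.67–6 × ULN has SD 4.33 × ULN/√12, or 131–162 U/L for an assumed ULN of 105–130 U/L.

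If correlation instead decays purely with time, the gain is nil. With time decay plus modest measurement error, variance falls 1.5–5% and power rises 0.4–1.5 points.

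**3. Simulation with the screening rules.** Log ALP is patient level plus random-walk drift plus independent visit noise. Patients are kept if Visits 1 and 2 lie within 1.67–6 × ULN and Visit 2/Visit 1 is at most 1.2. Noise and drift are scaled so that the SD of Week 12 minus Week 0 is 80 U/L in those kept.

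- Arms 12/8/20/12; visits at −7, −3, 0, 1, 4, 8 and 12 weeks; complete data.
- Unstructured MMRM with Week 0 ALP by visit; the screening mean enters as a main effect; df = n − p − 1.
- Nine settings: ULN 118, median 2.2 × ULN, log SD 0.5; plus all combinations of ULN 105/130, median 1.8/2.5 × ULN and log SD 0.4/0.6. 20,000 runs each.

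f is the share of the change variance that is short-term noise; the rest is drift.

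| f | 90% CI width | Power change, 20 vs 20 (points) | Power change with cohort term (points) |
|---|---|---|---|
| 1 | 8–15% narrower | +3.9 to +8.9 | +5.7 to +11.4 |
| 0.75 | 6–9% narrower | +3.1 to +5.9 | not tabulated |
| 0.5 | 3–5% narrower | +2.0 to +3.3 | +2.3 to +3.9 |
| 0.25 | 1–1.5% narrower | +0.6 to +1.2 | not tabulated |
| 0 | 0.1% wider | −0.2 to +0.1 | −0.2 to 0 |

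In the central setting (20 vs 20), power goes from 84.5% to 92.0% (f = 1), 81.2% to 84.4% (f = 0.5) and 80.8% to 80.7% (f = 0). Null rejection was 9.4–10.5% in all models. A separate large-sample Week 12 ANCOVA in the central setting narrowed the CI by 14.0%, 8.9%, 4.6%, 1.5% and 0% down the table, inside or at the edge of each range.

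**4. If the redacted terms hold an ALP category.** With a Week 0 category, the CI gains are unchanged. With a Visit 2 category, the CI is 5–12% narrower at f = 1 (+2.4 to +6.9 points) and 2–4% narrower at f = 0.5 (+1.1 to +2.8 points).

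**5. If fluctuation persists.** With a time constant of 4 weeks the CI is 3–5% narrower; with 10 weeks, 0.2–1%; with 20 weeks there is no gain.

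**The case against.** The strongest objection is that this is a preference whose value rests on figures absent from the documents. They give no within-patient correlation for ALP, and the result runs from slightly worse to clearly better. **This stands**: the size is an assumption, shown as a range that includes zero.

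The f = 1 figures are demanding. They need no drift over 19 weeks and independent visit noise of about 13–20% on the log scale, so exclusion criterion 45 would by chance alone remove about 15–23% of patients within the ALP limits. **This stands too**; the rows with f at or below 0.5 are the safer guide.

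The MMRM term list is redacted, so more may be adjusted for than can be read. This is a condition on the suggestion rather than a refutation.

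The assumed visit times put Visit 2 three weeks before Week 0, the widest gap the schedule allows. Moving Visits 1 and 2 to −5 and −1 weeks cuts both ways in the central setting. With a Week-12-specific slope, the gain under 4-week persistence falls from 8.0% to 5.6%; the f = 0.5 gain rises from 4.6% to 5.7%. Dropout is not modelled, and the simulation's df only approximate Kenward-Roger.

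It may also be too late. The SAP is approved, and Protocol 10.3.7 makes Cohort A data available to Lilly. If the study team has seen unblinded data, only a supplementary analysis remains.

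**Conclusion.** The point holds as an optional, low-cost improvement; the plan contains no error here. In the readable text, two required pre-randomisation measurements of the primary variable are left out of its analysis.

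The gain is useful if most 12-week variation is short-term fluctuation, small if half is drift, and nil if all is drift or if fluctuation persists for many weeks. The downside is bounded: with no extra information in the screening values, the 90% CI widens by 0.1% in the MMRM and 0.7–0.8% in the Week 12 ANCOVA. Confidence in the size is moderate. It rests on the assumed noise models, complete data, an SD of change of 80 U/L and the unredacted model not already holding a continuous screening ALP value.

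**What to change.** Check the unredacted model. If it has no continuous screening ALP value, add to SAP 6.2 and 6.1.3:

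- Keep Week 0 as the baseline for change and as a covariate with its visit interaction.
- Add the mean of Visit 1 and Visit 2 ALP as one continuous main effect, without a visit interaction, in the ALP MMRM and the supplementary ANCOVA.
- **Repeats.** Protocol 6.2 says "the tests may be repeated once during screening, and values resulting from repeat testing may be accepted for enrollment eligibility"; use the repeat value accepted for eligibility.
- **Rescreening.** Protocol 6.4 says "Individuals may be rescreened 1 time"; use the screening episode that led to randomisation.
- **Gaps.** Use a single screening value if only one exists, and Visit 1 alone if Visit 2 serves as baseline.
- **Timing.** Fix this before any unblinded data, including Cohort A summaries, reach the study team. Otherwise label it supplementary.
- Confirm that Visit 2 uses the full chemistry panel. Protocol Appendix 2, note b, describes an abbreviated panel without ALP; the schedule assigns it to no visit, and Protocol 5.1 requires ALP twice.

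The responder definition and the safety baseline stay as they are.

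The cost is a short paragraph, one parameter and no new samples. In the ANCOVA the worst case is variance up to about 2% higher and at most 0.9 power point lost. A main effect alone also recovers less than a Week-12-specific slope when fluctuation lasts weeks (time constant 4 weeks: 3–5% narrower instead of 4–8%). That is the price of a model fixed in advance.
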